10.3 Toxicity of Trabectedin

Trabectedin is given as standard of care and does have notable toxicities. The following are to be considered expected toxicities of trabectedin:

- Leukopenia (with neutropenia as the predominant component)
- Malaise
- Infection/sepsis
- Transaminase Elevation
- CK elevation
- Bilirubin or Alkaline phosphatase elevation
- Fatigue
- Nausea/vomiting
- Renal toxicity

Rhabdomyolysis is an unusual but well-described toxicity of trabectedin. If rhabdomyolysis is observed in a single case, this should not be considered a DLT but if multiple cases are seen, this must be reviewed by the DSMB.

10.4 Dose Modification of Trabectedin

Trabectedin is to be started at 1.5 mg/m². After the first week, the dose may be reduced if clinically indicated for toxicity management. Dose reductions will be noted in the subject's clinical record or research shadow chart.

As per standard practice, the subjects first dose reduction will be to 1.2 mg/m² and the second dose reduction will be to 1 mg/m². Dose reductions beyond 1 mg/m² are not permitted. If a subject is unable to tolerate a dose of 1mg/m², they must come off study. Trabectedin may be spaced out initially to 4 weeks and then to 5 weeks, as needed for toxicity management. If, in the opinion of the treating investigator, trabectedin needs to be spaced out greater than 5 weeks, Sponsor-Investigator approval is required.

Trabectedin dose reduction is required for the following adverse reactions:

- ANC < 1000/μL with fever and infection
- ANC <500/μL lasting > 5 days
- Platelets < 25,000/ μL
- Grade 3 or higher nausea and vomiting that persists despite a full anti-emetic regimen
- Grade 3 transaminitis not recovering to <2.5 x ULN or subject's baseline by 3 weeks post infusion
- Grade 3 Alk Phos Elevation not recovering to <2.5 x ULN or subject's baseline by 3 weeks post-infusion
- Total Bilirubin > 2.5 x ULN (direct bilirubin can be used if there is suspicion for Gilbert's syndrome)
- CK > 2.5 x ULN
- EF <45%

Subjects receiving the 1mg/m² dose of trabectedin with liver involvement from their cancer or baseline liver dysfunction, who are otherwise tolerating treatment well and appear to be benefiting from treatment on the study, may continue at the 1mg/m² after recovery from their liver dysfunction to grade 2, with Sponsor-Investigator approval.

11.0 SUBJECT DISCONTINUATION OF ACTIVE TREATMENT

Subjects may be removed from this study at any time at their discretion. Subjects may also be removed from this protocol if they develop any untoward side effects from the study medications.

If a subject withdraws consent to participate in the study or aspects of the study, attempts should be made to obtain permission to record survival data up to the protocol-described end of the subject follow-up period. Documentation in the medical record

or source should state that the subject is withdrawing from the study and what, if any, selected data the subject will permit the investigator to obtain.

An explanation for discontinuing treatment is recorded for each subject discontinuing treatment in the subject's medical record or research shadow chart. The Sponsor-Investigator must be notified immediately if a subject discontinues treatment. All subjects, irrespective of treatment status, will continue to be followed for survival. Treatment in this study must be discontinued for any of the following reasons:

- if the Sponsor-Investigator decides to stop the study;
- at Investigator's discretion;
- at the subject's request;
- if the subject enrolls in a trial of another investigational agent;
- Grade 4 or life-threatening toxicity (See Section 9, Adverse Events) attributable to study agent, unless otherwise addressed;
- progression;
- pregnancy.

A subject that enters hospice care will be considered withdrawn from the study. Adverse events will no longer be monitored or recorded. If the subject experiences a serious adverse event related to study treatment prior to withdrawal, this event will be followed to resolution or recovered with sequelae. Subjects and their families will no longer be contacted, however survival status may be obtained via electronic medical record or public database.

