8.0 SUBJECT EVALUATION

8.1 Screening Evaluations

This study will be conducted at the Fred Hutchinson Cancer Research Center, Seattle, USA. Each subject who enters into the screening period for the study receives a unique subject identification number before any study-related procedures are performed. The subject identification number will be assigned. This number will be used to identify the subject throughout the clinical study and must be used on all study documentation related to that subject.

The subject identification number must remain constant throughout the entire clinical study; it must not be changed after initial assignment, including if a subject is rescreened.

Before subjects may be entered into the study, the site must obtain written IRB/IEC approval for the protocol, informed consent form, and all other subject information and/or recruitment material, if applicable. A signed and dated Institutional review Board (IRB) approved informed consent form (latest approved version) must be obtained from each subject prior to performing any study-specific procedures. All subjects or legally authorized representatives must personally sign and date the consent form

before commencement of study-specific procedures. Adverse events are to be collected for a subject once they have signed informed consent through 90 days after the End of Treatment visit.

Screening evaluations will be performed for all subjects to determine eligibility. These evaluations must be obtained \leq 28 days prior to C1D1. Efforts should be made to complete screening procedures as close to initiation of protocol therapy as possible. Standard of care evaluations done prior to signing of consent may be used if they fall within the specified window prior to starting treatment.

A subject is considered enrolled when the investigator decides that the subject has met all eligibility criteria and upon completion of an eligibility review packet. The investigator is to document this decision and date, in the subject's medical record and/or in/on the electronic case report form (eCRF). Subjects should initiate treatment within 7 days of being enrolled to the study, and within the 14 day screening window from time of informed consent.

The following procedures are to be completed during the screening period, after signed informed consent has been obtained, designated in the Schedule of Assessments found in **Appendix C**.

- Informed Consent
- Demographics and Medical History

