8.5 Long Term Follow-Up / 90 Day Safety Assessment

AEs will be monitored and recorded in the subject's medical chart and research shadow chart from the time of first exposure to the investigational product avelumab, through 90 days (+/- 7 days) following last dose of a study drug. AEs with an onset date prior to the first exposure to an investigational product will not be followed, except in the case of clinically significant worsening of the AE during the specified AE monitoring time frame. Given the potential risk for delayed immune-related toxicities, safety follow-up must be performed up to 90 days after the last dose of avelumab administration. The extended safety follow-up beyond 30 days after last avelumab administration may be performed either via a site visit or via a telephone call with subsequent site visit requested in case any concerns noted during the telephone call.

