9.7 Adverse Event Recording Period

AEs will be monitored and recorded in the subject's medical chart and research shadow chart from the time of first exposure to the investigational product avelumab, through 90 days following last dose of a study drug. AEs with an onset date prior to the first exposure to an investigational product will not be followed, except in the case of clinically significant worsening of the AE during the specified AE monitoring time frame.

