9.7.1 Extended safety follow-up

- Given the potential risk for delayed immune-related toxicities, safety follow-up must be performed up to 90 days after the last dose of avelumab administration.
- The extended safety follow-up beyond 30 days after last avelumab administration may be performed either via a site visit or via a telephone call with subsequent site visit requested in case any concerns noted during the telephone call.

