19.3 APPENDIX C: Study Calendar

Study Flow Chart (for phase I portion)

Please note phase I and phase II schedules differ in that subjects on the phase I portion are required to be evaluated weekly up to week 7. Subjects on the phase II portion of the study and subjects on the phase I portion following week 7 are not required to be evaluated during weeks when they are not receiving therapy.

The study calendar will be managed in Weeks, with each dose of each drug being noted by a Cycle. For example, assuming there are no deviations from the planned schedule events, Week 1 will have Cycle 1 of avelumab and trabectedin. Week 3 will have Cycle 2 of avelumab, Week 4 will have Cycle 2 of trabectedin, Week 5 will have Cycle 3 of avelumab, Week 7 will have Cycle 4 of avelumab and Cycle 3 of trabectedin, etc. This may change based on dose delays or modifications. Weeks should be counted sequentially regardless of what number the dose of each agent is.

Treatment Week	Screening	1	2 ¹³	3	4	5	6 ¹³	7+ ¹⁰	EOT	30D Post EOT	90 Day Post EOT ¹²	LTFU ¹²
Scheduling Window (Days)		± 3	± 3	± 3	± 3	± 3	± 3	± 3	± 3	± 7	± 7	Q12W
Drug Administration ¹	None	A+T	None	A	T	A	None	A+T	None	None	None	
Echo/MUGA ²	X						X ²					
Informed Consent, IC/EC Review, Demographics and Med History	X											
Prior and Con-Med Review	X	X	X	X	X	X	X	X	X	X	X	
Post-study anticancer therapy status										X	X	X
Survival Status									X	X	X	X
Review Adverse Events		X	X	X	X	X	X	X	X	X	X	
Full Physical Examination (to include vitals, weight, ECOG)	X											
Directed Physical Examination (to include vitals, weight, ECOG)		X	X	X	X	X	X	X	X	X		
ECG (Phase 1 only)	X								X	X		
Pregnancy Test – Serum (WCBP Only) ³	X	X		X		X		X ³	X	X		
PT/INR and aPTT	X											
CBC with Differential, Blood Chemistry ⁵	X ⁵	X	X	X	X	X	X	X	X	X		
Urinalysis	X											
CK	X	X			X			X ⁶	X	X		
T3, FT4 and TSH ⁷	X							X ⁷	X	X		
Tumor Imaging ⁸	X							X ⁸	X ⁸			
Archival Tissue Collection (slides) ¹¹	X											
Correlative Studies Blood Collection ⁹		X		X		X		X ⁹	X			

¹A= Avelumab, T = Trabectedin. Avelumab is administered every 2 weeks. Trabectedin is administered every 3 weeks for Cycle 1 and 2 (Week 1 and Week 4), and every 4 weeks after that (Week 7, Week 11, Week 15,...). Trabectedin may be given every 5 weeks if required due to toxicity (see section 9). Please reference Section 7 for additional details.

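### Section 11 stops adverse event recording at hospice entry, while the 90-day safety windows and the SAE reporting rule carry no hospice exception

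*Combined protocol and SAP*

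**What the plan says.** Section 11.0 makes hospice entry a withdrawal from the study: "A subject that enters hospice care will be considered withdrawn from the study. Adverse events will no longer be monitored or recorded". It also says "Subjects and their families will no longer be contacted". Two things survive. A treatment-related SAE that arose before withdrawal is followed to its outcome, and survival status may be taken from the electronic medical record or a public database.

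Other sections set the period of safety collection without mentioning hospice:

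- Section 8.1 collects AEs from consent "through 90 days after the End of Treatment visit".
- Section 8.5 records AEs "through 90 days (+/- 7 days) following last dose of a study drug".
- Section 9.7 records them "through 90 days following last dose of a study drug".
- Section 9.7.1, citing delayed immune-related toxicity, says that "safety follow-up must be performed up to 90 days after the last dose of avelumab administration". Beyond 30 days this "may be performed either via a site visit or via a telephone call".
- Section 9.8.3 requires all SAEs to be reported to the manufacturer until the study is complete.
- The Appendix C calendar marks the row "Review Adverse Events" at 90 days after end of treatment.

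**The concern.** Safety graded by CTCAE is a primary endpoint (Section 3.1.2). For a subject who enters hospice soon after the last dose, site staff have two instructions: stop recording, or continue to day 90. If they follow Section 11.0, three kinds of information are lost:

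- AEs and SAEs with onset after entry.
- Worsening of AEs already present at entry, other than a related SAE still being followed.
- Cause and attribution of a death. The fact of death can still be found in records, but nothing asks whether treatment contributed.

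Hospice entry follows decline, so subjects who leave safety observation this way are probably not typical of the rest. The cut-off therefore depends on outcome, and event rates computed as if all subjects had been observed to day 90 could be too low. The 90-day period exists to catch late immune-related events, which are among those an early cut-off would miss.

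**Working it through.** The plan gives no figure to reproduce here. The check is a comparison of text, followed by a note on scale.

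**1. How far each rule runs, and whether hospice is excepted**

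| Place | What continues | End point | Hospice exception |
|---|---|---|---|
| Section 8.1 | AE collection | 90 days after End of Treatment visit | none |
| Section 8.5 | AE recording | 90 days (± 7) after last dose of a study drug | none |
| Section 9.7 | AE recording | 90 days after last dose of a study drug | none |
| Section 9.7.1 | safety follow-up | 90 days after last avelumab | none |
| Section 9.8.3 | SAE reporting to manufacturer | completion of the study | none |
| Appendix C calendar | AE review | 90 days post EOT | none |
| Section 11.0 | related SAE from before entry only | outcome of that SAE | is the hospice rule |

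The only other mention of hospice is in Section 9.2, which says that admission to hospice is not a hospitalization for SAE purposes. That does not limit the collection period.

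**2. Is hospice entry a withdrawal of consent?** No. Section 11.0 deals with consent withdrawal separately and asks which data the subject still permits. Hospice subjects are withdrawn by protocol rule.

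**3. Does the carve-out close the gap?** No. It covers neither new events nor non-serious ones. Its reach also depends on what related means. Section 9.8.3 counts events that may be related, while Section 9.6 treats possibly related AEs as unrelated for general AE assessment, which would make the carve-out narrower.

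**4. Is there a route for follow-up?** Sections 8.5 and 9.7.1 and the calendar footnote name a site visit or a telephone call. Section 11.0 rules out contact with subject or family. If the 90-day requirement applies, no named route remains after hospice entry.

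**5. Scale.** The documents give no hospice rate, entry time or survival after entry, so expected loss cannot be derived. For a single subject, take entry t days after last dose and survival of s days after entry, both assumed. Days of follow-up lost = min(90 − t, s):

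- t = 14, s = 14: min(76, 14) = 14 days, 14/90 = 16% of the window.
- t = 30, s = 30: min(60, 30) = 30 days, 30/90 = 33%.
- t = 14, s = 60: min(76, 60) = 60 days, 60/90 = 67%.

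These show what one case could mean and do not estimate the trial's loss. The planned total is 22, up to 34 (Section 4.2). One subject whose only occurrence of an event is missed lowers that event's crude rate by 1/22 = 4.5 points, or 1/34 = 2.9 points.

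**The case against.** The best defence is that Section 11.0 is a deliberate special rule. It is detailed: it defines status, stops recording, keeps one kind of SAE follow-up, bars contact and names sources for survival. Section 15.4 likewise mentions only survival status for withdrawn subjects who cannot or will not continue assessments. A specific rule is naturally read as overriding general ones, and on that reading no follow-up is required and no route is needed.

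This stands in part, so it would be too strong to say that the sections cannot be reconciled. But no window section refers to Section 11.0 or excludes withdrawn subjects, Section 9.7.1 is mandatory, and Section 9.8.3 runs to the end of the study rather than of the subject's participation. A deliberate exception would lose the same data.

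It is also fair that the listed sections are not all independent. Section 8.5 largely repeats 9.7 and 9.7.1, Section 9.7.1 speaks of safety follow-up, and Section 9.8.3 concerns reporting to the manufacturer. The route wording is permissive and applies beyond day 30, and Section 8.4 accepts documented efforts when the 30-day visit cannot be held.

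A reader might infer that dose-limiting toxicities (DLTs) would be missed and dose decisions altered. The documents do not support that firmly. Section 4.1.2 makes an at least possibly related death a DLT and puts enrollment on hold for any grade 5 toxicity, but its general DLT window is 6 weeks and it does not say whether that limit applies to deaths. Section 16.2 defines DLTs as unexpected and probably related. Eligibility requires a life expectancy of at least 6 months and good performance status (Section 5.1), which makes very early hospice entry less likely. An effect on the DLT count is a possibility only.

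**Conclusion.** The point holds as a gap in safety data collection. As written, Section 11.0 ends AE recording at hospice entry while the 90-day windows and the SAE reporting rule make no such exception, and the documents do not say which governs. If Section 11.0 is followed, events that begin or worsen after entry and within 90 days of last dose go unrecorded, and a death may lack cause and attribution. The loss is related to outcome and affects a primary endpoint.

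The size is unknown. It depends on how many subjects enter hospice within 90 days and how long they live afterwards, and the documents give neither. The objective response rate test is not affected.

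A reader might also infer bias in overall survival. That is not supported: Section 11.0 says all subjects remain in survival follow-up, and records may be used after hospice entry. Only the permissive wording there needs tidying.

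This is a cheap improvement. The mismatch in the text is certain; its practical effect is not.

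**What to change.** Reconcile Section 11.0 with Sections 8.1, 8.5, 9.7, 9.7.1 and 9.8.3 and with the Appendix C calendar and its footnote on extended follow-up:

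1. Keep the no-contact rule. Reword Section 11.0 so that hospice entry ends visits and contact, not data collection. The statement that these subjects count as withdrawn has to change too; otherwise data would be collected on subjects the protocol still calls withdrawn.
2. From records available to the site, collect any AE or SAE with onset or worsening through 90 days after last dose, plus cause of death and attribution where the records show them.
3. Name chart review as the route for these subjects in Sections 8.5 and 9.7.1 and in the calendar footnote.
4. State how the differing anchors (End of Treatment visit, last study drug, last avelumab, study completion) apply to them.
5. As clarification only, make record-based survival status something that will be obtained rather than may be.

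The cost is a protocol amendment with IRB approval, possible re-consent of enrolled subjects (Section 18.8), and modest chart look-up work. It adds no visits or family contact. Some hospice records will be incomplete, so some causes of death and attributions will stay unknown.

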12.0 CONCOMITANT MEDICATIONS

All medications taken at the start of the study will be documented/recorded in in the subject's medical record or research shadow chart.

12.1 Pre-Medication Treatment with Trabectedin and Avelumab

Pre-medication: Subjects will receive avelumab by IV infusion following pretreatment with H1 blockers and acetaminophen once every 2 weeks. Premedication with an antihistamine and with paracetamol (acetaminophen) (for example, 25-50 mg diphenhydramine and 500-650 mg paracetamol [acetaminophen] IV or oral equivalent) 30 to 60 minutes prior to the first four (4) doses of avelumab. Premedication may be discontinued for Cycle 5 and beyond of avelumab, at the investigator's discretion. This regimen may be modified based on local treatment standards and guidelines as appropriate provided it does not include systemic corticosteroids.

Likewise, trabectedin is a moderately emetogenic chemotherapy and anti-emetics should be given according to standard of care including 20 mg dexamethasone IV given at 20-30 minutes before trabectedin. Alterations to the dexamethasone route of administration may be allowed with Sponsor-Investigator approval. Outside of this pre-medication recommended in the trabectedin package insert, corticosteroids use is discouraged when not absolutely necessary and is not allowed for the treatment of trabectedin associated nausea and vomiting unless the subject has tried and failed to control their nausea with 2 prior anti-emetic regimens. Additional information regarding premedication and administration schedule is noted in Section 7.0.

12.2 CYP3A4 Inhibitors and Inducers with Trabectedin

It is notable that trabectedin is metabolized through CYP3A4. All inhibitors or inducers of cytochrome CYP3A4 (see below) should be noted prior to study entry.

Inhibitors of CYP3A4 include but are not limited to:

- aprepitant
- clarithromycin
- clotrimazole

- diltiazem
- erythromycin
- fluconazole
- grapefruit juice
- indinavir
- itraconazole
- ketoconazole
- nefazodone
- nelfinavir
- ritonavir
- saquinavir
- telithromycin
- troleandomycin
- verapamil

Inducers of CYP3A4 include but are not limited to:

- barbiturates
- phenytoin
- carbamazepine
- rifabutin
- rifampin
- St. John's Wort

Should a subject start on any of these drugs, dose modifications of trabectedin may be considered in consultation with the pharmacy and at the discretion of the subjects treating physician.

Inactivated vaccines, including inactivated flu vaccines, are allowed on study. All other vaccinations that include live-virus components are prohibited for subjects on while on study.

13.0 CONTRACEPTION

Avelumab may have adverse effects on a fetus in utero. Furthermore, it is not known if avelumab has transient adverse effects on the composition of sperm.

Contraception guidance and definitions are provided in Appendix E.

14.0 DATA AND SAFETY MONITORING PLAN

Institutional support of trial monitoring will be in accordance with the FHCRC/University of Washington Cancer Consortium Institutional Data and Safety Monitoring Plan. Under the provisions of this plan, FHCRC Clinical Research Support (CRS) coordinates data and compliance monitoring conducted by consultants, contract research organizations, or FHCRC employees unaffiliated with the conduct of the study. Independent monitoring visits occur at specified intervals determined by the assessed risk level of the study and the findings of previous visits per the institutional DSMP.

In addition, protocols are reviewed at least annually and as needed by the Consortium Data and Safety Monitoring Committee (DSMC), FHCRC Scientific Review Committee (SRC) and the FHCRC/University of Washington Cancer Consortium Institutional Review Board (IRB). The review committees evaluate accrual, adverse events, stopping rules, and adherence to the applicable data and safety monitoring plan for studies actively enrolling or treating subjects. The IRB reviews the study progress and safety

information to assess continued acceptability of the risk-benefit ratio for human subjects. Approval of committees as applicable is necessary to continue the study.

The trial will comply with the standard guidelines set forth by these regulatory committees and other institutional, state and federal guidelines.

